## 208 7. Analysis of the Secondary Endpoints

### 209 7.1 Included Subjects

210 In the analyses involving HbA1c and BMI standard deviation score, all subjects with an  
 211 available measurement within the analysis windows specified in section 7.3 will be included.

212 For secondary CGM metrics, inclusion criteria will be the same as the primary analysis.

213 For the secondary insulin outcomes computed during the main study, at least 168 hours of insulin  
 214 data in at least one period will be required for inclusion. If a subject has more than 168 hours of

215 insulin data in period 1 and then drops out of the study without any data in period 2, then he or  
216 she will be included in the analysis.

217 For the secondary insulin outcomes calculated during the extension phase, analyses will include  
218 participants with at least 168 hours of insulin data during the SAP phase of the main study and at  
219 least 672 hours of insulin data during the extension phase.

## 220 **7.2 Missing Data**

221 For the secondary CGM and insulin metrics, missing data will not be imputed in this study.

222 In the event that a BMI standard deviation score or HbA1c is unavailable at the end of a period  
223 but is available at a previous time point, it will be estimated using the method of direct likelihood  
224 to incorporate information from previous measurements to calculate the maximum likelihood  
225 estimate.

226 It is worth noting that all statistical methods for handling missing data rely on untestable  
227 assumptions and there is no one correct way to handle missing data. Our goal is to minimize the  
228 amount of missing data so that the results will not be sensitive to which statistical method is  
229 used.

## 230 **7.3 Analysis Windows**

231 Only HbA1c and body weight measurements obtained within  $\pm 7$  days of the end of treatment  
232 visit dates during each period will be included in the analyses as the outcome. The baseline  
233 measurements must be within  $\pm 14$  days of the recruitment visit.

234 During the extension phase, only HbA1c and body weight measurements occurring within  $\pm 7$   
235 days of the target collection dates will be included in tabulations of summary statistics every  
236 three months.

## 237 **7.4 Statistical Methods**

### 238 **7.4.1 Secondary CGM Outcomes**

239 For all secondary CGM outcomes, summary statistics appropriate to the distribution will be  
240 tabulated by treatment group over the four month period. Analysis of all secondary CGM  
241 endpoints will parallel the primary analysis. A ranked normal score transformation will be  
242 applied to all highly skewed secondary outcomes.

243 In the extension phase, summary statistics appropriate to the distribution will be tabulated for the  
244 secondary CGM metrics during the SAP period of the main study and during the extension  
245 phase. Summary statistics also will be tabulated every three months. Additionally, secondary  
246 CGM metrics will be compared between the extension phase and the SAP period of the main  
247 study using a paired t-test. For skewed outcomes, a nonparametric test will be used instead.

### 248 **7.4.2 Secondary Insulin Outcomes**

249 For all secondary insulin outcomes, summary statistics appropriate to the distribution will be  
250 tabulated by treatment group over the four month period. Analysis of all secondary insulin  
251 endpoints will parallel the primary analysis. A ranked normal score transformation will be  
252 applied to all highly skewed secondary outcomes.

253 In the extension phase, summary statistics appropriate to the distribution will be tabulated for the  
254 secondary insulin metrics during the SAP period of the main study and during the extension  
255 phase. Additionally, secondary insulin outcomes will be compared between the extension phase  
256 and the SAP period of the main study using a paired t-test. For skewed outcomes, a  
257 nonparametric test will be used instead.

258 **7.4.3 Secondary HbA1c Outcomes**

259 For HbA1c, a longitudinal model adjusting for period as a fixed effect will be constructed to  
260 compare treatment arms. The model will include three time points: (1) baseline, (2) period 1  
261 outcome, and (3) period 2 outcome. Summary statistics for HbA1c will be tabulated every three  
262 months during the extension phase.

263 **7.4.4 Secondary Clinical Outcomes**

264 For BMI standard deviation score, a longitudinal model adjusting for period as a fixed effect will  
265 be constructed to compare treatment arms. The model will include three time points: (1) baseline,  
266 (2) period 1 outcome, and (3) period 2 outcome.

267 **7.5 Secondary Analyses by Time of Day**

268 Summary statistics for the following outcome metrics will also be tabulated separately for  
269 daytime (defined as 8am to less than 12am) and nighttime (defined as 12am to less than 8am)  
270 over the four month period and during the extension phase:

- 271 • Percent time with glucose levels spent in the target range (3.9 to 10.0 mmol/L)
- 272 • Mean of glucose levels
- 273 • Standard deviation of glucose levels
- 274 • Percent time with glucose levels below 3.9 mmol/L
- 275 • Total insulin dose

276 For each of these outcome metrics during the main study, the same model described above for  
277 the primary and secondary analyses will be fit with the inclusion of a treatment by time of day  
278 interaction. The same subjects will be included as in the primary analysis. The p-value for the  
279 interaction term will be reported. These analyses will be conducted to determine whether a  
280 similar trend to the overall treatment effect is seen in the different times of day.

281 The study is not expected to have sufficient statistical power for definitive conclusions in the  
282 secondary analyses by time of day, and statistical power will be low to formally assess for the  
283 presence of a treatment by time of day interaction. Interpretation of the analyses by time of day  
284 will depend on whether the overall analysis demonstrates a significant treatment effect. In the  
285 absence of any significant treatment effects in the overall analyses, assessment of secondary  
286 analyses by time of day will be considered exploratory and used to suggest hypotheses for  
287 further investigation in future studies.

288 **7.6 Questionnaire Analyses**

289 For each questionnaire (and their corresponding subscales), total scores will be calculated and  
290 reported at each time point. They will also be compared between treatment arms using the same  
291 model described above for the primary outcome. The distribution of responses for each

292 individual question at baseline and for each treatment arm will also be reported in separate  
293 tables.

294 For the INSPIRE Survey, a mean score will be calculated instead of a total score. The mean  
295 score will be calculated after excluding all questions where the participants give a response of  
296 "NA".

297 For the Pittsburgh Sleep Quality Index (and all of its subscales), the scoring instructions will be  
298 used to calculate the total scores overall and by subscale. For this questionnaire, scores will be  
299 tabulated for each parent who completes the survey.

300 For the INSPIRE Survey and the CL Experience Survey, a treatment arm comparison will not be  
301 done, because the surveys are only completed at the end of the CL arm. For these questionnaires,  
302 only summary statistics for the scores and the distribution of responses for each question will be  
303 reported. Additionally, treatment arm comparisons will not be done for the Pittsburgh Sleep  
304 Quality Index or the Children's Sleep Habit Questionnaire, because they are only completed at  
305 visit 8.

306 For the Strengths and Difficulties Questionnaire, no overall total score will be calculated that  
307 involves every question. Instead, only a Total Difficulties Score is computed from the questions  
308 comprising the Emotional Problems, Conduct Problems, Hyperactivity, and Peer Problems  
309 subscales.

310 The electronic data capture system for this study will not allow the subject to submit any  
311 questionnaires until all items are completed. Analysis will be limited to subjects who submit a  
312 questionnaire (no imputation).

313 **7.7 Ancillary Analyses**

314 Cost utility analyses and human factors analyses will be described in a separate document.

315 **8. Safety Analyses**

316 All safety outcomes will be tabulated by participant for all events from enrollment to the final  
317 study visit.

318 **8.1 Definitions**

319 Reportable adverse events for this protocol include any untoward medical occurrence,  
320 unintended disease or injury, or untoward clinical signs (including abnormal laboratory findings)  
321 in a subject who has received an investigational device, whether or not related to the  
322 investigational medical device. These include severe hypoglycemia (SH) and diabetic  
323 ketoacidosis (DKA).

324 Hypoglycemic events will be considered severe if the event requires assistance of another person  
325 due to altered consciousness to actively administer carbohydrate, glucagon, or other resuscitative  
326 actions. This means that the subject is impaired cognitively to the point that he/she is unable to  
327 treat him- or herself, is unable to verbalize his or her needs, is incoherent, disoriented, and/or  
328 combative, or experiences seizure or coma. If plasma glucose measurements are not available  
329 during such an event, neurological recovery attributable to the restoration of plasma glucose to

330 normal is considered sufficient evidence that the event was induced by a low plasma glucose  
331 concentration.

332 Definite DKA is defined as having all of the following:

- 333 • Hyperglycemia (blood glucose >200 mg/dL or >11 mmol/L)
- 334 • with either low pH (<7.3) or low serum bicarbonate (<15 mmol/L)
- 335 • and ketonemia or ketonuria

336 **8.2 Adverse Events Summary**

337 All episodes of SH and of DKA along with any other reportable adverse events will be listed by  
338 treatment group.

339 Separate listings will be provided for pre-randomization and post-randomization adverse events.  
340 A separate listing also will be provided for events that occur during the extension phase.

341 **8.3 Comparison of Safety Outcomes between Treatment Groups**

342 The following safety analyses will be performed if enough events occur for formal statistical  
343 analyses.

344 For each of the following safety outcomes, mean  $\pm$  SD or summary statistics appropriate to the  
345 distribution will be tabulated by treatment group:

- 346 • Number of subjects with any DKA events
- 347 • Number of episodes of DKA events per subject and incidence rate per 100 person years
- 348 • Number of subjects with any SH events
- 349 • Number of episodes of SH events per subject and incidence rate per 100 person years
- 350 • Number of adverse events per subject
- 351 • Number of serious adverse events per subject

352 All of the above safety outcomes will be tabulated for all subjects (including dropouts and  
353 withdrawals), regardless of whether CGM data are available or whether the closed loop system  
354 was operational (if the event occurred during the CL period). Any adverse events that occurred  
355 before the treatment initiation visit in period 1 or during the washout period will not be included  
356 in the rate calculations or treatment group comparisons listed above. In all safety analyses, each  
357 period will inclusively consist of all days in between the treatment initiation visit and the end of  
358 treatment visit. If the subject drops out of the study in the middle of a period and the end of  
359 treatment visit for that particular period does not occur, then the dropout date will be used as the  
360 last day of the period.

361 The number of person-years for the incidence rate calculations in each period will be inclusively  
362 defined as the number of person-years in between the treatment initiation visit date and the end  
363 of treatment visit date. If the subject drops out of the study in the middle of a period and the end  
364 of treatment visit for that particular period does not occur, then the dropout date will be used as  
365 the last day of the period.

366 For each of DKA and SH (if enough events), the event rates will be compared using a repeated  
367 measures Poisson regression model adjusting for period and whether the subject has ever had a

368 prior event. Binary variables will also be compared using a repeated measures logistic regression  
369 model adjusting for period and whether the subject has ever had a prior event.

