## **9.13 End of 2nd Study Arm (Visit 8b)**

Sixteen weeks after the start of the second treatment arm (Visit 7) subjects will have completed the primary study phase. Study devices will be downloaded. A blood sample will be taken for measurement of HbA1c (see section 12.2.1). Body weight and height measurements will be made. Parents/carers will be asked to complete questionnaires (see section 12.3). Parents/carers who were interviewed at the end of the 1st arm of the study will be re-interviewed (see section 12.4).

This will be the end of the primary phase 8-month study period and subjects who are not continuing with the extension phase will return to their normal diabetes care. These subjects/guardians will be asked to return the study devices used, and will revert to their conventional insulin therapy by switching back to the insulin pump they were using before entering the study.

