# **12 Methods and Assessments**

## **12.1 Procedures**

### **12.1.1 Height and Weight**

These will be recorded at the study initiation visit at baseline and at the end of each study arm. Those participating in the extension phase will have height and weight recorded at 18 months after the primary phase final study visit. Height will be measured in centimetres using calibrated measuring devices. Weight will be measured in kilograms using a calibrated electronic scale.

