#### CGM derived indices:

- Standard deviation, and coefficient of variation of glucose levels
- Time with glucose levels <3.5 mmol/L (63 mg/dL) and <3.0 mmol/l (54 mg/dl)
- Time with glucose levels in significant hyperglycemia (glucose levels > 16.7 mmol/l) (300 mg/dl)
- AUC of glucose below 3.5 mmol/l (63 mg/dl) and below 3.0 mmol/l (54 mg/dl)

448 Insulin and Other Endpoints:

- BMI standard deviation score
- Total, basal, and bolus insulin dose

451 Questionnaires:

- Strengths and Difficulties Questionnaire
  - Emotional Problems Subscale
  - Conduct Problems Subscale
  - Hyperactivity Subscale
  - Peer Problems Subscale
  - Prosocial Subscale
  - Total Difficulties Score
- Hypoglycemia Fear Survey
  - Behavior Subscale
  - Worry Subscale
- WHO-5
- Epworth Sleepiness Scale

464 Analyses by Time of Day:

- Percent time with glucose levels spent in the target range (3.9 to 10.0 mmol/L)
- Mean of glucose levels
- Standard deviation of glucose levels
- Percent time with glucose levels below 3.9 mmol/L
- Total insulin dose

470 During the extension phase, Benjamini-Hochberg false discovery rate (FDR) adjusted p-values  
471 will be calculated within these subcategories:

472 CGM derived indices and HbA1c metrics:

- Time spent above target glucose (10.0 mmol/l) (180 mg/dl)
- HbA1c at 18 months
- Average of glucose levels
- Time spent below target glucose (3.9 mmol/l) (70 mg/dl)
- Standard deviation, and coefficient of variation of glucose levels
- Time with glucose levels <3.0 mmol/l (54 mg/dl)
- Time with glucose levels in significant hyperglycemia (glucose levels > 16.7 mmol/l) (300 mg/dl)

481 Insulin and Other Endpoints:

- BMI SDS
- Total, basal, and bolus insulin dose

484 Questionnaire Scores:

- Strengths and Difficulties Questionnaire
- Hypoglycemia Fear Survey
- WHO-5
- Epworth Sleepiness Scale

489        • INSPIRE Survey  
490

491 **14. Exploratory Analyses**  
492 No exploratory analyses will be performed for this study.  
493

494 **15. Additional Analyses after Version 2.0 and Clarifications of Previous  
495 Analyses**

496 **15.1 Post-Hoc Secondary Insulin Outcomes in Units/kg/day**  
497 Secondary insulin outcomes as previously outlined in section 7.4.2 were reported and tested in  
500 Units/day. Post-hoc analysis of secondary Insulin outcomes in Units/kg/day will parallel the  
501 primary analysis. A ranked normal score transformation will be applied to all highly skewed  
502 secondary outcomes.

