503 Insulin outcomes measured in U/kg/day will be treated as missing for a period if either the  
504 insulin dose or the patient's weight is missing for that period. Previous measurements will not be  
505 used to impute missing values

506 Benjamini-Hochberg false discovery rate (FDR) adjusted p-values will be calculated. Post-hoc  
507 secondary insulin outcomes in Units/kg/day will be added to the *Insulin and Other Endpoints*  
508 subcategory previously defined in section 13.2. Subcategory for FDR correction will now  
509 include the following seven (7) outcomes:

510        • Old analyses:  
511             BMI standard deviation score  
512             Total insulin (Units/day)  
513             Basal insulin (Units/day)  
514             Bolus insulin (Units/day)  
515        • New analyses:  
516             Total insulin (Units/kg/day)  
517             Basal insulin (Units/kg/day)  
518             Bolus insulin (Units/kg/day)

519 **15.2 Post-Hoc Secondary Insulin Outcomes in Units/kg/day by Time of Day**

520 Secondary total insulin outcome by time of day as previously outlined in section 7.5 was  
521 reported and tested in Units/day. Post-hoc analysis of secondary total insulin outcome in  
522 Units/kg/day will parallel the primary analysis, with the inclusion of a treatment by time of day  
523 interaction. The p-value for the interaction term will be reported. A ranked normal score  
524 transformation will be applied to all highly skewed secondary outcomes.

525 Where weight is missing at a follow-up visit, insulin outcomes in U/kg/day will be treated as  
526 missing.

527 Benjamini-Hochberg false discovery rate (FDR) adjusted p-values will be calculated. Post-hoc  
528 secondary insulin outcomes by time of day in Units/kg/day will be added to the Analyses by Time  
529 of Day subcategory previously defined in section 13.2. Subcategory for FDR correction will  
530 include the following six (6) outcomes:

531     • Old analyses:

532         ○ Percent time with glucose levels spent in the target range (3.9 to 10.0 mmol/L)  
533         ○ Mean of glucose levels  
534         ○ Standard deviation of glucose levels  
535         ○ Percent time with glucose levels below 3.9 mmol/L  
536         ○ Total insulin dose (Units/day)

537     • New analysis:

538         ○ Total insulin (Units/kg/day)

539

540 **15.3 Post-Hoc Secondary Tabulation by Time of Day**  

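### The extension insulin comparison has no correction for growth, and the Units/kg/day analysis added in SAP version 3.0 is not specified for it

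*Combined protocol and SAP*

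**What the plan says.** For the UK-only extension, SAP 7.4.2 says: "Additionally, secondary insulin outcomes will be compared between the extension phase". The comparator is the main-study pump period. The method is a paired t-test, or a nonparametric alternative if the outcome is skewed. There is no term for weight, age or calendar time, and the single-arm extension has no concurrent control.

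Neither 7.4.2 nor the endpoint list in SAP section 4 gives a unit for insulin dose. The unit appears in SAP 15.1, added in version 3.0: "Secondary insulin outcomes as previously outlined in section 7.4.2 were reported and tested in". The unit that completes this sentence is Units/day. The section then adds post-hoc per-kg outcomes, such as "Total insulin (Units/kg/day)", analysed in the same way as the primary endpoint. They join a false-discovery family said to "include the following seven (7) outcomes". Under 15.1 a per-kg value is missing for a period if the dose or the weight is missing, and earlier measurements are not used to fill it.

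The extension family in SAP 13.2 contains BMI SDS and total, basal and bolus insulin dose, with no per-kg outcome. On weights, protocol 12.1.1 says: "Those participating in the extension phase will have height and weight recorded at 18 months after the primary phase final study visit". Main-phase weights are taken at baseline and at the end of each arm.

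**The concern.** In the crossover, growth is handled by design: treatment order is randomised and the model has a period term. In the extension the comparison always runs from earlier to later. If insulin need rises with body size, a child whose dose per kg never changes still shows a higher daily dose in the extension, and a paired test on Units/day cannot separate that rise from an effect of prolonged closed-loop use.

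Three of the four tests in the extension's insulin and other endpoints family are exposed. The fourth, BMI SDS, is already standardised for growth through the WHO chart (SAP 4.2). At stake is a reported insulin increase under closed loop that is partly or wholly growth.

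**Working it through.** The plan gives no effect size or power for the extension insulin endpoints, so there is no figure of its own to reproduce. The check has four steps.

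**1. Time gap.** Inputs: 16-week arms (protocol 9.13: "Sixteen weeks after the start of the second treatment arm (Visit 7) subjects will have completed the primary study phase"), washout of 1 to 4 weeks (protocol 6), and an extension of 548 days (SAP 4.1), with its midpoint at day 274 after Visit 8b. The midpoint of an arm is day 56.
- Pump arm second: 56 + 274 = 330 days (10.8 months).
- Pump arm first: 56 + 112 + 7 + 274 = 449 days (14.8 months) with a 1-week washout; 56 + 112 + 28 + 274 = 470 days (15.4 months) with a 4-week washout.

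Visit windows widen the range to about 9.9-16.8 months. All this takes data to be spread over the whole extension; the inclusion minimum is only 672 hours (SAP 7.1).

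**2. Growth over the gap.** Assumptions not in the documents: body weight 18-20 kg, gain of 1.5-2.5 kg/year, dose proportional to weight. Relative growth = rate × (gap/365.25) / weight.
- Low end: 1.5 × 330/365.25 / 20 = 6.8%.
- High end: 2.5 × 470/365.25 / 18 = 17.9%.

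The total dose in KidsAP01 with standard-strength insulin was 18.4 U/day (protocol 4.3.2). The shift is 18.4 × 0.068 = 1.2 U/day to 18.4 × 0.179 = 3.3 U/day, with dose per kg unchanged. Under proportionality, basal and bolus shift by the same percentages.

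**3. Chance that growth alone gives p<0.05.** Two UK sites at 8-12 children each give at most 16-24; take n = 20. The two-sided paired t-test has 19 degrees of freedom and noncentrality shift × √20 / SD, where SD is the assumed SD of the paired difference.

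| Growth shift | SD 3 U/day | SD 5 U/day |
|---|---|---|
| 1.2 U/day | 0.40 | 0.17 |
| 2 U/day | 0.81 | 0.40 |

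The nominal rate is 0.05. For the 2 U/day shift, n = 16 to 24 gives 0.70-0.88 (SD 3) and 0.32-0.47 (SD 5).

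**4. What a per-kg test needs.** With weights matched to the dose windows, proportional dosing gives a change of zero. Mismatched weights do not:
- Pump dose divided by end-of-arm weight and extension dose by a mid-extension weight leaves 56 days of growth: 1.5 × 56/365.25 / 20 = 1.2% to 2.5 × 56/365.25 / 18 = 2.1%, still upward.
- Pump dose divided by end-of-arm weight and the pooled extension dose by the 18-month weight alone biases the result downward, by about 3% at 5% growth per year and 8% at 15%.

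**The case against.** The strongest objection is that the extension's unit is inferred. A reader might take 15.1 as a statement that the extension is tested in Units/day; it does not go that far. It is in the past tense, in a version dated May 2021 and marked as written after the initial analyses, while the last extension participant was expected in October 2022 (protocol 23). It most naturally reports the main-phase analyses. Since it refers to 7.4.2 as a whole, one can also argue that the per-kg addition extends to the extension.

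That stands as a limit on certainty but does not remove the problem. The seven-outcome list uses the main-study label for BMI, the missing-data rule is written by period, 15.3 is confined to the four-month period, and 13.2's extension list is unchanged. Even on the generous reading, no weight is defined for the extension dose and nothing withdraws the Units/day tests.

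Other points also stand. Protocol 14.4.2 calls these endpoints exploratory, and confounding with time is inherent in a single-arm extension. Growth rate, body weight, proportional dosing and SD are outside assumptions. The 18.4 U/day was measured under closed loop, not pump therapy. The probabilities use unadjusted p-values, whereas SAP 13.2 plans false-discovery adjustment. If 3 and 5 U/day were instead the SD of each measurement, with independent errors, the SD of the difference would be 4.24 or 7.07 and the 2 U/day probabilities would fall to about 0.52 and 0.22, still above 0.05.

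**Conclusion.** The concern holds in this form: the extension insulin comparison is a before-after test without a growth term, Units/day is the only unit the SAP ties to it, and Units/kg/day is not specified for it. Under the stated assumptions, growth alone accounts for about 7-18% of dose, and it raises the chance of a nominally significant increase well above 0.05.

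Three stronger inferences are not supported. Growth does not make significance certain: at 1.2 U/day with SD 5 the probability is about 0.17. The extension's primary conclusion is not at risk, because that endpoint is time in range. And the children concerned are not the trial's full 1-to-7 range: UK entry starts at age 2 (protocol 7.1.1). The point is worth correcting but does not threaten the trial's main results.

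**What to change.** In SAP 7.4.2 and the extension list in 13.2, make total, basal and bolus dose in Units/kg/day the tested outcomes, and report Units/day descriptively without a p-value.

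Define a weight matched in time to each dose window. For the pump period, interpolate by date between the scheduled weights on either side (baseline and Visit 6, or Visit 6 and Visit 8b). For the extension, interpolate between Visit 8b and Visit 9, which is their mean when data cover the full 18 months. Treat the per-kg value as missing if a needed weight is missing, in line with 15.1.

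Reconcile the weight schedule at the same time. SAP 7.3 expects three-monthly extension weights within 7 days of target; protocol 12.1.1 schedules weight at 18 months only, and Visit 9 has a window of 6 weeks either side.

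The cost is document wording, since the weights needed for these tests are already scheduled. The small downside is that children without a Visit 9 weight drop out of these exploratory tests.
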